8.4. Randomization Criteria

The following randomization criteria must be satisfied at the Visit 2 Baseline Randomization Visit in order for the patient to be eligible to continue in the study. Only those patients meeting all of the following randomization criteria are eligible for randomization:

1. Patient continues to meet all inclusion and exclusion criteria, including urine and blood test results, and
2. Visit 2 total CAPS-5 score ≥ 33 ("Symptom Severity version using 1-week recall), and

3. At Visit 2, patient is not severely depressed (based on the investigator's judgment and Visit 2 C-SSRS, CAPS-5, and BDI-II, and considering the pre-randomization collaborative review by the investigator and medical monitor(s) of the patient's Visit 1 psychiatric history, presenting symptomatology, M.I.N.I. 7.0.2, C-SSRS, CAPS-5, and BDI-II assessments).
4. No active suicidal intent or plan, based on Investigator's judgment, and Visit 2 C-SSRS responses (e.g., no C-SSRS Type 4-5 ideation or suicidal behavior since Visit 1).

8.5. Prior and Concomitant Medications

Many concomitant medications are prohibited during this study because this study has been designed to evaluate the safety and efficacy of monotherapy with TNX-102 SL tablets for the treatment of PTSD. The goal of the study is to recruit patients who are not currently using other medications to treat their PTSD, or who are not clearly benefitting from any of the medications that would need to be discontinued in order to enter this study. Since many patients with PTSD may already be taking one or more excluded medications when screened, Principal Investigators should use extreme caution when determining whether a patient, in their clinical judgment, can be safely withdrawn from current medications that are being used to treat PTSD or are otherwise excluded from the protocol.

Eligible patients will not be receiving treatment with antidepressants, antipsychotic agents, mood stabilizers or anticonvulsants. In addition, eligible patients will not have taken antidepressants within 2 months of the Baseline visit. This time frame is intentionally long because it is not considered appropriate for patients to discontinue antidepressants solely to enter the study. An exception is made for the use of low-dose tricyclic agents at doses ≤ 25 mg per day, or trazodone at doses ≤ 150 mg per day, either of which may be discontinued for the purpose of enrollment but requires a 1-week medication-free period prior to randomization, as described below.

Patients also must be willing and able to discontinue use of benzodiazepines, non-benzodiazepines and certain other medications frequently used to treat PTSD; e.g., prazosin; trazodone; topiramate. Discontinuation of any of these agents should only be considered if/when the patient's clinical condition and stability will not be adversely affected.

Unless otherwise stated, excluded medications (e.g., trazodone, prazosin, topiramate, alpha-adrenergic agonists or antagonists [e.g., prazosin; tamsulosin; terazosin; doxazosin, silodosin, alfuzosin, clonidine, guanfacine], buspirone, benzodiazepines, and non-benzodiazepine hypnotics [zolpidem, zaleplon, eszopiclone]) will require a 1-week drug-free period prior to the Baseline visit (Visit 2). Similarly, all opioid medications, including tramadol and tapentadol, are excluded medications. Patients on chronic opioids are not appropriate candidates for participation, but there may be patients with occasional PRN opioid usage or who were recently on a short course for acute pain who may be appropriate if, in the clinical judgement of the Investigator, they could be safely tapered and remain opioid free for the week before baseline visit and throughout the 12 weeks of the study. The screening period of up to 35 days is provided to ensure a safe tapering rate and discontinuation of excluded medications, per Investigator's discretion, leading up to the 1-week medication-free period required before the randomization/baseline visit.

Other medications capable of modifying the pharmacologic activity of TNX-102 SL (e.g., α -adrenergic agonists/antagonists; potent CYP3A4 inhibitors) will also be excluded, and discontinuing these medications should only be considered if clinically acceptable. A list of CYP3A4 inhibitors is provided in [0](#); only those considered potent or strong inhibitors (in the left-hand column) are excluded medications.

8.5.1. Allowed Concomitant Medications

It is ideal to have all patients participating in the study go without any hypnotic agents for the entire double-blind period of the study. Yet there may be instances in which patients' insomnia symptoms need to be addressed with a concomitant treatment. In these instances, the Investigator should recommend use of an antihistamine-based OTC hypnotic, such as Benadryl[®] or generic diphenhydramine 25-50 mg, for a limited period (e.g. no more than a few nights in a row). Patients should be asked to keep track of their use of such sleeping remedies, and again, chronic nightly use should be avoided whenever possible.

Melatonin is considered an allowable concomitant medication but its usage should have been stable for at least 30 days prior to baseline and usage should remain stable during the study. If diphenhydramine is ineffective, the treating Investigator should contact the medical monitor to discuss alternative options.

Allergy medications and cold remedies containing adrenergic agonist decongestants such as pseudoephedrine or phenylephrine should be avoided unless absolutely necessary (and in such cases when considered absolutely necessary, they should be avoided in the evening or at bedtime to minimize their interference with sleep). Sympathomimetics such as adrenergic agonist decongestants have the potential to acutely worsen PTSD symptoms and therefore could confound the assessment of TNX-102 SL versus placebo for treatment of PTSD.

Other prescription or over-the-counter medications not specifically excluded by entry criteria typically may be continued during the study, with the expectation that chronic medications should have been used in a stable fashion for at least 30 days prior to randomization. Sites should contact the medical monitor for any questions about whether a concomitant medication may be continued during the study or if it would be acceptable to taper an excluded medication.

8.6. Withdrawal Criteria

In accordance with the Declaration of Helsinki, human patients have the right to withdraw from the study at any time for any reason. The investigator and Tonix also have the right to remove patients from the study. Additional information regarding withdrawal or discontinuation of patients is described in detail in [Section 10.5.1](#).

9. STUDY DRUG MATERIALS AND MANAGEMENT

9.1. Study Drug Packaging, and Labeling and Storage

Study drug supplies will be packaged identically so as to maintain the integrity of the study blind. The study medication bottles will be labeled minimally with the following information: study number TNX-CY-P301, sponsor name and address, bottle number, quantity, storage

conditions, usage instructions, and caution statements for investigational new drug, i.e., Caution: New Drug Limited by United States Law to Investigational Use, and Keep Out of Reach of Children and Pets.

Each study medication bottle will contain 40 tablets. Two bottles will be dispensed to each patient at Visit 2 (baseline), Visit 4 (Week 4) and Visit 5 (Week 8); this will provide the patient with 80 tablets to cover the 4 weeks of dosing between visits, plus additional tablets to cover loss and/or visit window variability. The patient should be instructed to take all the tablets in one bottle before opening the second bottle. The patient should be instructed to keep this study medication in a safe location out of extreme environmental conditions and out of the reach of children and pets, and be instructed that this medication is not to be taken by any individual other than the study patient. Each patient will also be instructed that they will be expected to return both bottles and all unused study medication at each clinic visit; unused medication will be counted to assess compliance with study drug treatment.

Storage of the study drug at the investigational site should be under locked and secure conditions with limited staff access. Study drug should be stored at 20-25°C/68-77°F in a temperature/humidity-monitored room; however, brief excursions (15-30°C/59-86°F) as defined in the Study Reference Manual (IP Receipt and Storage) are permitted without the sponsor's approval.

9.2. Dosing Instructions

Patients will be instructed to take **two** tablets of their assigned study drug (TNX-102 SL 2.8 mg tablets or placebo tablets) sublingually, placed simultaneously **under the tongue**, each evening at bedtime starting at bedtime on evening of Day 0 (Day of Visit 2) and continuing without interruption for 12 weeks. The study drug should be taken at bedtime after teeth brushing and other oral care has been completed. The mouth/sublingual area should be moist at the time of dosing, so the patient should drink a few sips of water prior to dosing, especially if prone to dry mouth. Patients will be instructed to place the two SL tablets under their tongue and keep them there until they have dissolved. They should not swallow, crush or chew the tablets. Patients should not eat or drink (or chew gum) for at least 15 minutes after dosing, and preferably not until morning. Patients will be reminded that only 2 (two) tablets are allowed per day. Note: In the event that the patient misses a dose, instruct the patient to continue dosing with two (2) tablets the next evening; i.e., they should not take more to make up for the missed dose.

9.3. Dispensing Instructions

Each patient who has met the randomization criteria ([Section 8.3](#)) will be assigned 2 double-blind treatment bottles at Visit 2 via the IWRS, with a unique, but otherwise random bottle number that is generated when the study coordinator successfully completes randomization procedures. Patients will also be assigned two new treatment bottles at Visits 4 and 5 via the IWRS. The bottle numbers provided by the Interactive Web Response (IWR) system at these visits will tell the site which treatment bottles have been assigned to the patient.

In the event of loss of study medication, new medication will be provided by the IWR system, when appropriately requested by the site and/or the sponsor or designee.

Study treatments for the double-blind treatment phase are either:

Treatment A: 2 × TNX-102 SL 2.8 mg tablets (“TNX-102 SL”) to be taken sublingually once daily at bedtime.

Treatment B: 2 × placebo tablets (“placebo”) to be taken sublingually once daily at bedtime.

9.4. Release of Clinical Study Supplies to the Investigator

Tonix or Tonix’s designee’s standard operating procedures for releasing clinical trial supplies to the site will be followed.

9.5. Study Drug Accountability and Reconciliation

All patients will be expected to bring their bottles of study medication with them to all study visits. At each study visit, the site staff will inspect the medication bottles, and perform a count of the tablets remaining in the bottles and document this in the patient’s record. An assessment of medication adherence should be done by the study staff to ensure that the patient understands all dosing instructions and is taking the medication as prescribed. Patients will be asked for an explanation if the count of returned study drug tablets indicates a discrepancy between the expected number of tablets dosed and the number returned in the bottles. If it is found that the patient is not taking the study medication as expected, the patient will be re-counseled with instructions, and this should be noted in the patients’ records. A deviation should be recorded on any patient who is less than 70% compliant with dosing between visits.

If the patient fails to return any of the unused study drug as expected, the patient should be questioned regarding the reason for the lower than expected tablet number and about potential misuse, abuse or diversion. If more than 8 tablets cannot be accounted for at any of the visits where drug is returned (week 4, 8 or 12), the investigator will be asked to evaluate the situation, and a written summary of this evaluation should be added to the source and entered onto the case report form (CRF). Situations where replacement drug is requested, or when more than 8 tablets cannot be accounted for, should be recorded as deviations.

All study medication, including partial and empty bottles, must be maintained at the study site until Tonix or its designee verifies drug accountability and provides instruction for destruction or the return of the investigational product to the Sponsor’s drug distribution depot.

Tonix or their designee will perform drug accountability which entails reconciliation between the amount of drug shipped to the study site, study drug assigned and dispensed to the patient (including returned unused assigned study drug), and study supplies that were never dispensed and/or assigned to patients.

10. STUDY VISITS AND PROCEDURES

The overall and detailed schedule for study procedures and visits is provided in [Appendix 1](#).

10.1. Visit 1 (Screening: Day -35 to -7)

10.1.1. Informed Consent

Before the potential patient has undergone any study-related screening procedures, including any downward titration or withdrawal of medications, the nature of the study and the potential risks associated with it will be explained to the patient, and the patient will be given an opportunity to ask questions to his or her satisfaction. After all questions are answered, but before proceeding further, the patient must read and sign a written informed consent form. This signed informed consent form will be retained in the Investigator's study file, and the date the patient signed the form will be entered into the Case Report Form (CRF). The patient will be provided with a copy of his or her signed and dated informed consent form. The patient will be required to sign all updated informed consents. Separate written, signed informed consent must be obtained if the patient is to participate in the post-study pharmacogenomic assessment.

10.1.2. Screening Overview

Screening Visit 1 will start a variable length screening period. The length of the screening period is to be no shorter than 7 days, but may be as long as 35 days in order to accommodate medication taper and discontinuation or other study requirements.

If the patient is eligible to continue in the study, and does not need to discontinue any excluded medication, the patient may be scheduled to return for Visit 2 (Randomization) in 7 (or more) days, assuming all screening evaluations have been completed, including confirmation of acceptable laboratory and ECG results. If the patient needs to undergo taper and discontinuation of excluded medication, the Investigator will generate a written down titration schedule for the patient and will schedule Visit 2 such that the date of Visit 2 is at least 1 week after the date of the final dose of any excluded medication. If additional clinic visits are deemed necessary by the investigator for clinical monitoring of the patient before scheduling Visit 2, such visits will be recorded as unscheduled visits.

10.1.3. Patient Numbering

All screened patients will be assigned a unique concatenated 6-digit site-patient number (e.g., 102-112) by the IWR system. A screening log or system documenting the following information will be recorded and maintained, and will include the patient's initials, screening number, whether the patient was ultimately randomized or not, and if not randomized, the reason the patient was excluded/screen-failed.

10.1.4. Screening and Assessments/Procedures

The following screening assessments/procedures will be completed in the following general order:

- Obtain written informed consent to participate

- Obtain demographics, including alcohol, nicotine/tobacco (smoking and/or chewing), and marijuana use
- Obtain medical history
- Obtain prior and current medication history, including all prior PTSD therapies and other treatments for psychiatric indications
- Obtain psychiatric history (M.I.N.I. 7.0.2)
- Administer PTSD Rating Scales:
 - Life Events Checklist (LEC-5)
 - Criterion A – Assessment Form (CA-AF)
 - Clinician Administered PTSD Scale (CAPS-5) (Since Last Month version)
- Perform physical examination, including visual inspection of the oral cavity (including floor of mouth/sublingual area)
- Obtain vital signs, height, weight and BMI
- Draw samples for clinical laboratory tests for:
 - Chemistry, hematology, HIV and TSH, with free thyroxine also performed if TSH is outside the upper or lower limits of normal
 - Urine Drug Screen (central laboratory)
 - Serum pregnancy test (for women of child-bearing potential)
- Conduct 12-lead electrocardiogram
- Administer Depression/Suicidality Scales
 - Beck Depression Inventory (BDI-II)
 - Columbia Suicide Severity Rating Scale (C-SSRS, Baseline/Screening Version, with rater review of BDI-II prior to starting C-SSRS interview)
- Review inclusion/exclusion criteria

Only those patients meeting all of the inclusion and none of the exclusion criteria will be eligible to continue. NOTE: Final determination of eligibility based on clinical laboratory tests will be made when results have been returned.

Sites will be asked to complete and submit to the Tonix medical monitoring team key screening information. This information will be reviewed by the Tonix medical monitoring team to help ensure the selection of well-qualified patients. The specific requirements and timelines associated with this pre-randomization review process will be outlined in a separate document.

Once eligibility has been confirmed and authorization for randomization granted by a Tonix medical monitor, eligible patients will return to the clinic for Visit 2.

There is no requirement for Follow-Up visits for patients who are screen failures. Patients who fail to qualify should have their medication adjusted, as appropriate, per the judgment of the

Investigator and be released from the clinic. There will be no requirement to enter data into the electronic case report form (eCRF) for patients who are not randomized.

10.2. Visit 2 (Baseline: Day 0)

Visit 2 should be scheduled 7 to 35 days after Visit 1. Study procedures will be completed (including qualifying baseline assessments for the C-SSRS and CAPS-5). If the patient meets all randomization criteria, the patient will be randomized via the IWR system to receive double-blind study medication.

10.2.1. Pre-Randomization Assessments

The following assessments must be completed at Visit 2 to confirm that the patient is eligible for randomization. Upon arrival at the clinic, the following assessments should be done, preferably in this order:

- Assess occurrence of adverse events
- Update medical history (with changes since screening noted)
- Assess changes in medication history and concomitant medications
- Obtain vital signs and weight
- Administer CAPS-5 - “Symptom Severity Version”, using 1-week recall
- Conduct urine drug screen (urine dipstick, only as necessary, if select Visit 1 tests were positive for excluded medications that required discontinuation prior to randomization)
- Conduct urine pregnancy test (for women of child-bearing potential)
- Perform visual examination of the oral cavity
- Have the patient complete the following outcome scales (in order):
 - SDS
 - PROMIS scale for sleep disturbance
 - MTRSS (assessment of sedation)
 - CSFQ-14
 - BDI-II (needs to be completed prior to the C-SSRS and reviewed by the C-SSRS rater at outset of C-SSRS interview)
- Administer the C-SSRS- Since Last Visit Version (with rater review of BDI-II prior to starting C-SSRS interview)

10.2.2. Randomization Criteria

Once all pre-randomization assessments have been completed, only those patients who meet all of the following randomization criteria will be eligible to continue:

1. Patient continues to meet all inclusion and exclusion criteria, including urine and blood test results, and

2. Visit 2 total CAPS-5 score ≥ 33 (“Symptom Severity” version using 1-week recall), and
3. At Visit 2, patient is not severely depressed (based on the investigator’s judgment and Visit 2 C-SSRS, CAPS-5, and BDI-II, and considering the pre-randomization collaborative review by the investigator and medical monitor(s) of the patient’s Visit 1 psychiatric history, presenting symptomatology, M.I.N.I. 7.0.2, C-SSRS, CAPS-5, and BDI-II assessments).
4. No active suicidal intent or plan, based on Investigator’s judgment, and Visit 2 C-SSRS responses (e.g., no C-SSRS Type 4-5 ideation or suicidal behavior since Visit 1).

If the patient does not satisfy these randomization criteria, the patient has failed to qualify for this study and should be considered a screen failure, with the reason documented. With Medical Monitor approval, if the patient is otherwise considered a qualified and compliant patient, Visit 2 may be delayed to accommodate situations in which extenuating or short-term circumstances do not warrant screen failure.

If the patient does satisfy these randomization criteria, then continue with the following:

- Randomize the patient via IWRS Randomization System
- Dispense 4-week supply (two bottles) of double-blind study medication
- Review patient instructions regarding study drug dosing ([Section 9.2](#))
- Schedule next study visit

10.3. Visit 3 (Telephone Visit: Day 14)

Visit 3 will be done as a telephone call to the patient and should be conducted after 2 weeks of treatment, on Day 14 \pm 3 days.

The following steps should be completed:

- Assess changes in concomitant medications
- Assess study drug compliance based on patient verbal report
- Assess occurrence of adverse events, including any oral adverse events and whether an unscheduled visit is indicated for an examination of the oral cavity
- Review patient instructions regarding drug dosing.
- Administer the ‘Since Last Visit’ C-SSRS

After all of the items have been reviewed with the patient, the patient should be given an appointment to return to the clinic for Visit 4, and be re-instructed, as necessary, on dosing instructions, and reminded to bring study medication back to the clinic at their next visit.

10.4. Visit 4 and 5 (Weeks 4 through 8)

Visits 4 and 5 are similar study visits that are scheduled to be conducted after 4 and 8 weeks of treatment, respectively. Visit 4 should occur on Day 28 \pm 5 days and Visit 5 should occur on Day 56 \pm 5 days.

The following assessments and procedures are scheduled for these visits in the following general order:

- Collect study drug and assess compliance
- Assess occurrence of adverse events
- Update concomitant medications
- Obtain vital signs and weight
- Administer CAPS-5-“Symptom Severity Version” using 1-week recall
- Conduct urine pregnancy test (for women of child-bearing potential)
- Have the patient complete the following outcome scales (in order):
 - SDS
 - PROMIS scale for sleep disturbance
 - MTRSS (assessment of sedation)
 - PGIC
 - BDI-II (needs to be completed prior to the C-SSRS and reviewed by the C-SSRS rater at outset of C-SSRS interview)
- Administer C-SSRS - Since Last Visit Version
- Physician to assess CGI-I (needs to be completed once all other assessments are available for investigator to review)
- Dispense new bottles of double-blind study medication as assigned by IWRS

After all of the assessments at each visit have been completed, the patient should be given an appointment to return to the clinic for the next scheduled visit, and be re-instructed, as necessary, on dosing instructions, and reminded to bring study medication back to the clinic at their next visit.

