Patients suffering from depression are eligible for the study, provided their depression does not pose an undue risk to their well-being (e.g., suicidal risk) or warrant treatment with

antidepressants or other excluded treatments. The investigator will evaluate each patient's medical and psychiatric history, current symptomatology, and the results of the MINI 7.0.2, BDI-II, C-SSRS, and CAPS-5 from Visits 1 and 2, to determine whether it is appropriate for the patient to participate in the study. In addition, each patient will undergo medical monitor pre-randomization review to ensure agreement with the investigator's assessment.

NOTE: Patients who use alcohol/marijuana but do not meet criteria for alcohol/substance use disorder (per Diagnostic and Statistical Manual of Mental Disorders [Version 5; DSM-5]) are otherwise suitable for the study provided that, in the judgment of the Investigator, this usage will not interfere with the patient's ability to complete the study or provide reliable data. Information related to marijuana and alcohol use will be collected at Screening.

Patients with evidence of hepatic impairment secondary to hepatitis B or C at screening, or who are undergoing treatment for hepatitis, should be excluded. Patients with stable and asymptomatic disease whose hepatic enzymes (aspartate aminotransferase [AST] or alanine aminotransferase [ALT]) satisfy the study's entry criteria (< 3 times the upper limits of normal), may be allowed to proceed with randomization with prior Medical Monitor approval.

CAPS-5, M.I.N.I. 7.0.2 and Columbia Suicide Severity Rating Scale (C-SSRS) interviews will be conducted by an approved and qualified individual(s) at each site who has successfully completed training on each instrument.

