10.5. Visit 6 (Week 12)

Visit 6 should occur after 12 weeks of double-blind study drug treatment, scheduled at Day 84 -5 / +7 days. The following assessments and procedures are to be completed in the following general order:

- Collect study drug and assess compliance
- Assess occurrence of adverse events
- Update concomitant medications
- Obtain vital signs and weight
- Administer CAPS-5-“Symptom Severity Version” using 1-week recall
- Conduct urine pregnancy test (for women of child-bearing potential). Serum pregnancy test may be done at Investigator’s discretion.

- Draw samples for clinical laboratory tests for:
 - Chemistry and hematology
- Perform visual examination of oral cavity
- Have the patient complete the following outcome scales (in order):
 - SDS
 - PROMIS scale for sleep disturbance
 - MTRSS (assessment of sedation)
 - PGIC
 - CSFQ-14
 - BDI-II (needs to be completed prior to the C-SSRS and reviewed by the C-SSRS rater at outset of C-SSRS interview)
- Administer C-SSRS-Since Last Visit Version
- Physician to assess CGI-I (needs to be completed once all other assessments are available for investigator to review)

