- Administer C-SSRS – Since Last Visit Version

If the patient withdraws after the week 2 (visit 3) visit window (on or after day 11), the following assessments and procedures are to be completed at this visit in the following general order:

- Document reason for early termination
- Collect study drug and assess compliance
- Assess occurrence of adverse events
- Update concomitant medications
- Obtain vital signs and weight
- Administer the CAPS-5-“Symptom Severity Version” using 1-week recall
- Draw samples for clinical laboratory tests for:
 - Chemistry and hematology
 - Serum pregnancy test (for women of child-bearing potential)
- Conduct visual examination of oral cavity
- Have the patient complete the following outcome scales (in order):
 - SDS
 - PROMIS scale for sleep disturbance

- MTRSS (assessment of sedation)
- PGIC
- CSFQ-14
- BDI-II (needs to be completed prior to the C-SSRS and reviewed by the C-SSRS rater at outset of C-SSRS interview)
- Administer C-SSRS- Since Last Visit Version
- Physician to assess CGI-I (needs to be completed once all other assessments are available for investigator to review)

Once these assessments have been completed, the patient may be discharged from the study, provided that there is no need for additional follow-up to continue to monitor an adverse event or other condition.

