11.2. Efficacy Assessments

The primary efficacy endpoint and many of the secondary and exploratory efficacy endpoints in this study are derived from clinician-administered assessments which must be administered by qualified and trained individuals at each clinical site. Study specific training will be required before staff is allowed to administer these scales. In an attempt to minimize variability in

responses of a given patient over time, it is important that the same rater administer the scales to a given patient throughout the study unless absolutely unavoidable due to the rater's absence from the clinic. It is also important that the assessments, including those that are patient-completed, be conducted in the specified order, according to specific instructions, and in a setting where the patient has minimal distractions, appropriate privacy and sufficient time to complete them.

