11.3.5. Visual Examination of Oral Cavity

A visual examination of the oral cavity should be done at Screening (Visit 1), Baseline (Visit 2) and after 12 weeks (Visit 6) of treatment and/or at Early Termination. In addition to these regularly scheduled examinations, a visual inspection of the oral cavity (including the sublingual area) should be done any time a patient spontaneously reports an oral adverse event (other than transient sensory AEs such as tongue numbness, tingling or bitter taste) to confirm presence or absence of any irritation or other signs. Additional details related to onset, duration, severity and reversibility of oral events will be documented in the CRF.

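### At every post-baseline visit with a CAPS-5, adverse event questions are listed before it, and neither document keeps the site rater from AE reports before scoring

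*Protocol*

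**What the plan says.** - **Order.** Protocol 10.4 introduces the list for Visits 4 and 5 with "The following assessments and procedures are scheduled for these visits in the following general order". Protocol 10.5 does the same for Visit 6 with "The following assessments and procedures are to be completed in the following general order". In both, "Assess occurrence of adverse events" comes before the CAPS-5. The list in 10.5.1 for early termination (ET) on or after day 11 has the same sequence.
- **Weight given to order.** Protocol 11.2 says it is important that the assessments "be conducted in the specified order, according to specific instructions".
- **Rater.** Protocol 7.1 has the CAPS-5 "conducted by an approved and qualified individual(s) at each site who has successfully completed training on each instrument". Sections 11.2 and 11.2.1 ask for the same rater for a patient at all visits. Section 11.2.1 leaves further instructions on conducting and scoring the CAPS-5 to separate material.
- **Oral sensory AEs.** Protocol 11.3.5 requires an oral inspection when an oral AE is reported, "other than transient sensory AEs such as tongue numbness, tingling or bitter taste". SAP 10.5 makes the same exception and describes such events as known to be sensory only.
- **Earlier disclosure.** The Week 2 telephone visit in Protocol 10.3 includes "Assess occurrence of adverse events, including any oral adverse events and whether an unscheduled visit is indicated for an examination of the oral cavity".

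**The concern.** The primary endpoint is the change in total CAPS-5 at Week 12, scored by a clinician in a semi-structured interview. Such a score leaves room for judgement. A rater who has just heard a patient report a numb tongue or a bitter taste may form a view about the assignment.

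If such reports are more frequent in one arm, that view is correlated with treatment, and any effect on scoring goes into the treatment difference. The planned analyses would not reveal it. The sensitivity analyses in SAP 9.1.2 concern missing data only, and no treatment-guess question or other check of blinding is planned.

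**Working it through.** The plan states no figure on this point, so the check compares passages.

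**Step 1. Position of each item in the visit lists.**

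| Visit | AE item | CAPS-5 item |
|---|---|---|
| Visit 2, baseline (10.2.1) | 1 | 5 |
| Visit 3, telephone (10.3) | 3 | not done |
| ET before day 11 (10.5.1) | 3 | not done |
| Visits 4 and 5 (10.4) | 2 | 5 |
| Visit 6 (10.5) | 2 | 5 |
| ET on or after day 11 (10.5.1) | 3 | 6 |

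Among the post-baseline visits with a CAPS-5 (Visits 4, 5, 6 and the later ET visit), AE questions come first in 4 of 4. Visit 3 and the earlier ET visit have no CAPS-5.

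**Step 2. What else precedes the CAPS-5.** Drug return is listed before it at all four. Under Protocol 9.5 a tablet-count discrepancy leads to a request for an explanation, and the answer may be a side effect. At the later ET visit the first item is the reason for termination, which can itself be an AE. The scheduled oral examination follows the CAPS-5 at Visit 2, Visit 6 and the later ET visit, and none is scheduled at Visits 4 and 5. Its position is not a problem.

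**Step 3. Is the rater separated from AE information?** Protocol 7.1, 11.2 and 11.2.1 require training and continuity of the rater. Neither document describes central rating or says that the rater must not take, hear or read AE reports. SAP 3.3 deals with treatment codes. The lists do not say who asks the AE questions.

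**Step 4. Are oral sensory AEs tied to an arm?** Protocol 11.3.5 and SAP 10.5 name them, and Protocol 10.5.2 gives oral hypoaesthesia as an example. None says which arm they occur in. Section 5.1.1, on prior clinical experience, is redacted. Placebo tablets are called identical (7.2) and packaging is identical (9.1), but a match on taste or oral sensation is not stated.

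**Step 5. Can the bias be sized?** The bias due to order would be the product of three quantities:

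- the difference between arms in the share of patients with a revealing AE report;
- the mean shift in CAPS-5 score that such a report causes;
- the fraction of that knowledge gained at the same visit rather than earlier.

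The documents give none of the three, so no figure follows from them.

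**The case against.** The case on the other side is substantial.

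- **The order is loose.** The lists are a general order. The sentence in Protocol 11.2 stands in a paragraph about rating scales and patient-completed instruments, so it does not clearly govern where AE questions fall. This stands. It is still true that a site following the lists as written asks about AEs first.
- **The rater may not hear the AE history.** No passage says that the CAPS-5 rater takes it, and the separate rater instructions may already keep the two apart. This stands too. The point is that the protocol and SAP leave the exposure open, not that it occurred.
- **Oral AEs may not reveal the arm.** A reader might infer that numbness, tingling and bitter taste mark active drug. The documents do not support that. They name these events when deciding if an inspection is needed, and give no rates by arm.
- **Order is only part of the route.** A reader might also multiply an assumed excess of oral AEs by an assumed rater shift and present the result as the cost of the order. Both inputs would be guesses, and the product would measure all functional unblinding through oral AEs. Visit 3 asks about oral AEs before any post-baseline CAPS-5, and the rater stays with the patient. Reordering does not undo an event already disclosed.
- **There are mitigations.** Protocol 11.3.1 asks for non-leading opening questions, and the AE step at Visits 4 to 6 has no oral prompt, unlike Visit 3. These reduce the exposure but do not remove it.

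**Conclusion.** The point holds as an avoidable risk, not as a demonstrated bias. The listed order puts AE questions before the CAPS-5 at all four kinds of post-baseline visit where it is scored, and neither document shields the rater from the answers.

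The risk becomes a bias only if three things are true: oral sensory AEs are more common on active drug, the rater learns of them before scoring, and that knowledge shifts the score. The public text establishes none of these, and the size is unknown.

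The change is worth making because the endpoint is clinician-rated, the planned analyses could not detect the problem, and the remedy costs little. The CGI-I, the first key secondary endpoint, is more exposed, since the investigator scores it once all other assessments can be reviewed. Moving the CAPS-5 does not alter that.

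**What to change.** 1. In Protocol 10.4, 10.5 and the day-11-onward list in 10.5.1, place the CAPS-5 before drug accountability and AE elicitation.
2. Give it the same position in 10.2.1 (Visit 2), so that baseline and follow-up ratings are taken under matching conditions.
3. State in 11.2.1 that the CAPS-5 rater does not ask about or review AE data before scoring. At the ET visit this should cover a reason for termination that is an AE. Where site staffing already allows, it should extend to AE data from Visit 3 and other earlier visits.
4. Leave the scheduled oral examination where it is.

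If the separate rater instructions already contain such a rule, the protocol should state it or refer to it. The synopsis estimates last patient completion in January 2019. If visits are over, what remains is to document who took the AE history and who scored the CAPS-5, and to report it.

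The cost is a revised visit checklist and one added sentence, with no extra staff or procedure. There are two drawbacks. Protection is partial, because the same rater may recall earlier AEs. AE questions asked after a long symptom interview may also be slightly primed by it.
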